### **Purpose**

The purpose of this study is to test new models of osteoporosis screening and treatment adherence on fracture risk in older men using a group randomized trial compared to no additional screening support (control). Randomization and intervention will occur at the Patient Aligned Care Team (PACT) level; therefore, the PACT providers will complete the informed consent process, agreeing that their team will utilize the randomly assigned care model. Because many PACT teams are located off site, we request a waiver of documentation of informed consent.

All care models deliver VA guideline-recommended osteoporosis screening and treatment to high-risk Veterans by DVAHS credentialed clinical staff, which represents usual clinical care. Patient-level measures are all routine clinical utilization and outcomes collected solely from the electronic medical record. Therefore, a waiver of informed consent and HIPAA authorization for the patient-level data collection procedures is requested as the study presents minimal risk beyond routine clinical care to Veterans.

### **Specific aims:**

1. Compare the impact of BHS primary osteoporosis screening models on **patient level outcomes** strongly associated with fractures as measured by the EHR at 2 years; 1) eligible proportion screened; 2) medication adherence (initiation; implementation, and discontinuation); 3) bone mineral density at the femoral neck in a random sample of high risk patients. Fracture rates (fractures/patient years) are exploratory.

H1a: PACT teams randomized to BHS will have better patient level outcomes compared to usual care at pre-specified clinically important levels, adjusting for baseline levels.

2. Determine the impact of BHS primary osteoporosis screening models on **provider and facility level outcomes** including change in DXA volume, change in metabolic bone disease clinic volume (assessed by EHR), and PACT provider time and satisfaction (assessed by Nominal Group Technique).

H2a: DXA and metabolic bone disease clinic volumes will increase during the intervention, with a higher proportion of referrals coming from PACTs randomized to BHS.

H2b: Provider satisfaction with osteoporosis screening systems will be higher for PACTs randomized to BHS management compared to usual care.

3. Determine the impact of BHS primary osteoporosis screening programs on **health system and policy level outcomes** using Markov models of screening program cost per quality adjusted life year. Model inputs are based on VA national fracture data from our prior work, results from aims 1 and 2, and published quality of life estimates.

### **Background and Significance**

Osteoporosis is under-recognized in older men. At age 50 years, 1 in 5 men can expect to suffer a major osteoporotic fracture in their remaining lifetime, comparable to the risk of prostate cancer. Men are more than twice as likely as women to experience complications after a fracture, and have greater excess mortality after hip fracture. Because risk factors are common in Veterans, osteoporosis is

particularly prevalent in the Veterans Health Administration (VA) system. More than half of male Veterans over age 50 years have osteopenia or osteoporosis, a rate nearly double the non-Veteran population.

Fractures resulting from osteoporosis have negative consequences on functional status, mortality, and quality of life, with high rates of pain, depression, and loss of independence. After a hip fracture, nearly 75% of patients spend time in a nursing facility, and only 20% regain their prior level of ambulation. Many fractures are associated with substantial excess mortality; men with a hip fracture have excess annual mortality of 20% that persists up to 10 years. Osteoporotic fractures also have an important economic impact. It is estimated that hip fractures result in 43 million dollars of excess cost to the VHA annually.

Fortunately, osteoporotic fractures are preventable. The generic bisphosphonate alendronate (annual VA cost VA \$20) reduces the risk of vertebral, hip and other non-vertebral fractures by 45%, 40%, and 16% respectively. Although fewer studies in men are available, fracture risk reduction has been similar. Importantly, our work shows that bisphosphonates also reduce mortality in men and women. Medication adherence is critical, but has been documented to be poor within VA and community settings.

Osteoporosis screening is simple and inexpensive. Patients without a prior fracture are selected for treatment based on the results of a non-invasive Dual Energy X-ray Absorptiometry (DXA) measurement of bone mineral density (BMD). Current U.S. guidelines suggest that it is cost-effective to treat patients with BMD T-score of  $\leq -2.5$  (osteoporosis), and those with T score between -1.5 and -2.5 (osteopenia) who have additional risk factors resulting in a 10 year fracture risk of over 3% for hip fracture, or 20% for major osteoporotic fracture.

Despite the high burden and preventability of osteoporotic fractures, men are rarely diagnosed or treated for osteoporosis before a fracture has occurred. Economic models based on large cohort studies have suggested that screening is likely to be highly cost-effective. Furthermore, our national VA cohort study (see preliminary studies) demonstrates screening effectiveness in high risk subgroups. Professional groups including the American College of Physicians, Endocrine Society, National Osteoporosis Foundation, the Canadian Medical Association, the U.K. Health System, and the VA Undersecretary for Health all advocate for primary osteoporosis screening in men.

Osteoporosis screening and treatment services within VA are ineffective overall. Our national study of primary osteoporosis screening in male Veterans (preliminary studies) showed wide variation in patient selection. Overall, screening rates were 8% for men over age 65; far lower than expected based on the prevalence of osteoporosis risk factors in the population. Moreover, even among men in whom screening was completed, it was not associated with lower overall fracture rates because osteoporosis treatment and adherence following screening were extremely low. The result is an **ineffective and wasteful primary osteoporosis screening program across VA** that does not identify appropriate men for screening, nor facilitate treatment adherence for those found to be at high fracture risk. Notably, we found that screening was associated with clinically important reductions in fractures for high-risk men in pre-specified subgroup analyses.

Attempts to improve osteoporosis screening using traditional quality improvement programs have been minimally effective. EHR alerts alone do not improve osteoporosis screening rates and do nothing to address adherence. However, two distinct osteoporosis screening paradigms have been suggested, and form the scientific premise for the models proposed in this application. A practice manager approach in which a non-physician staff member is responsible for organizing osteoporosis screening led to a doubling in osteoporosis screening in a single academic medical center, but its impact on medication adherence is unknown. In this paradigm, responsibility remains at the individual practice level (or in VA, PACT). In contrast, a Fracture Liaison Service (referred to here as "Bone Health Service", BHS) represents a centralized model that has been successful in improving secondary osteoporosis screening and treatment adherence after a fracture has already occurred. In this model, a team of nurses led by a bone specialist identify patients with fracture within the entire health system, and arrange for evaluation and treatment. Such models have reduced 2-year fracture rates by 56% and are cost saving or highly cost-effective. The National Bone Health Alliance and others recommend expansion of BHS models to address primary fracture prevention, however its impact on osteoporosis screening and treatment rates in this context are unknown.

Based on this body of evidence, we conclude that the VA urgently needs data on the impact of primary osteoporosis screening and adherence models to inform the adoption of rational clinical programs.

## Design

Pragmatic group randomized trial of PACT teams (n=39 teams recruited, estimated 24 at DVAHS and 15 at Richmond VAMC) will be randomized into 2 groups: a control group (no additional support, and a centralized Bone Health Service (BHS) model. Outcomes for all patients eligible for osteoporosis screening within the randomized PACTs will be assessed by investigators masked to group assignment via EHR at baseline and 2 years. Outcomes for PACT providers will be assessed using qualitative methods (nominal group technique).

**Outcome measures** are listed in the table 1 below.

Table 1. Outcome measures by Aim. RDW=Regional Data Warehouse; MPR=Medication Possession Ratio; FRAX=Fracture Risk Assessment Tool.

Outcome	Definition/Measure	Data Source/Timing	Important Difference
Patient (Panel) Level (Aim 1)			
Screening Rates	Proportion of eligible men screened in last 12 months	RDW at baseline, year 1 and year 2	25% increase from 6% Control
Medication Initiation	Proportion of screened men meeting treatment threshold (T score $\leq -2.5$ or FRAX score high-risk) who receive at least 1 prescription	RDW, intervention period year 1 and year 2, non-VA medication lists by chart abstraction.	30% increase from 55% Control
Medication Implementation	Days of medication dispensed divided by follow-up days	Pharmacy dispensing records, for patients started within prior year at baseline, year 1 and 2. Non-VA medication lists by chart abstraction.	20% increase in MPR $>80\%^{14}$ from 30% Control
Medication Discontinuation	Time between first prescription dispensing date and the date of first medication possession gap of $\geq 3$ months	Pharmacy dispensing records, for patients started within prior year at baseline, year 1 and 2. Non-VA medication lists by chart abstraction.	20% difference
Bone Mineral Density	BMD g/cm  at femoral neck and lumbar spine in random sample of men eligible for screening	Random sample of 712 men (356 UC, 178 each of the other 2 models) eligible for screening in panel at least 1 year, measured 2 years after start date	Post-intervention between group difference of 3% femoral neck, 5% lumbar spine 
Harms	Proportion of men started on oral medication for new GI distress in 3 months  Subtrochanteric fractures or Osteonecrosis of the jaw	RDW ICD10 codes, new prescription for proton pump inhibitor or H2 blocker.  RDW ICD10 codes	15% increase from 30% Control  >expected 1/50,000 patient years treatment
Fractures (exploratory)	All clinical fractures excluding facial, digital	RDW, confirmed by chart abstraction	10% decrease from 2.5/100 person years Control
Provider/Facility Level (Aim 2)			
DXA volume	DXA orders/ 1000 patients/year, by	EMR data, calculated at 2	

	intervention group	years	
Bone Disease clinic volume	Consults/ 1000 patients/year, by intervention group	EMR data, calculated at 2 years	
PACT satisfaction, time	Nominal Group Technique at Routine Staff meeting	Measured at 2 years	
Health System/Policy Level (Aim 3)			
Program Cost Effectiveness	Cost/quality adjusted life years (QALY) of the screening models compared to control	Markov model with above outcomes, fracture rates, cost and quality of life from VA and medical literature	Probability of cost/QALY >80% at thresholds of \$50,000, \$100,000, \$200,000 

**Provider-level Covariates** will be collected from the PACT providers at the time of randomization, including medical provider type (Advanced Practice Provider vs. MD), medical provider and RN years in practice, years in VA, and practice site (rural CBOC, urban CBOC, VAMC).

**Patient-level Covariates** will be extracted from the Regional Data Warehouse and CPRS.

Demographics include age, self-reported race, body mass index, and rural zip code as classified by Rural-Urban Commuting Area. Because medication co-pays may be a barrier to adherence, co-pay status will be collected. Co-morbidities related to fracture risk include chronic lung disease, diabetes, endocrine disorder (hyperthyroidism, hyperparathyroidism, Cushing's, hypogonadism), prostate cancer, rheumatoid arthritis, Parkinson's disease, stroke, gastrectomy/malabsorption, smoking, alcohol abuse, chronic kidney disease, chronic liver disease, dementia. Medications include calcium, vitamin D, glucocorticoids, androgen deprivation therapy, traditional anti-epileptic drugs, proton pump inhibitors, selective serotonin reuptake inhibitors, and psychoactive medications.

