#### **BHS Screening Promotion**

1. The Bone Health Nurse (BHS RN) will identify eligible patients quarterly as described previously. Patients will be contacted via letter and telephone, and if they agree will be scheduled for DXA.
2. The BHS RN obtains DXA results, calculates Fracture Risk Assessment Tool (FRAX) score, and those meeting treatment thresholds are referred to the Bone Health MD for e-consult.
3. The Bone Health MD reviews additional clinical information in the EHR and generates an e-consult containing recommendations for additional laboratory evaluation (if needed) and treatment; this note is co-signed by the PACT provider. The BHS RN then contacts the patient to provide education and shared decision making, and places orders for PACT provider co-signature.

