#### **BHS Adherence Promotion**

1. All patients initiating bisphosphonates will be called by the BHS RN at 1, 6, and 12 months to identify adherence barriers using a validated tool modified for osteoporosis therapy.

Algorithms for overcoming patient and health-care system adherence barriers to osteoporosis medications will be used in these calls (appendix 1). For example, patients reporting gastrointestinal distress will be offered annual intravenous therapy; patients with difficulty ordering refills will be assisted to enroll in *myhealththevet*. The 12-month call will ensure that the medication has been re-ordered. Subsequently, patients not refilling medications will be identified from RDW every 6 months, with telephone follow-up as indicated.

2. Patients with medication nonadherence identified during these calls will be offered an additional educational visit, based on the content of a prior successful osteoporosis adherence promotion program. The educational program will be delivered by the BHS RN during a group visit, Virtual Medical Room visit, or telephone visit at the Veteran's choice.

*Table 2. Model components by step in the Screen and Treat Process. All steps represent usual clinical care for the Veteran.*

Step in Process	Control	PACT Practice Management (removed from study activities)	Bone Health Service (BHS)
Screening Promotion			
Selection for screening	Discretion of provider	List of eligible patients provided to PACT RN biannually	BHS RN queries RDW quarterly
Scheduling screening	Provider orders; MSA or Veteran phone call to radiology	PACT RN orders; MSA or Veteran phone call to radiology	BHS RN orders and coordinates scheduling with Veteran
Quantify risk from DXA results, determine if they meet treatment threshold	Discretion of provider	Provider accesses FRAX link on Osteoporosis order set	BHS RN and BHS MD based on FRAX risk
Shared decision-making with Veteran	Provider by phone or at next primary care visit	Provider by telephone or at next primary care visit, patient education materials available	E-consult to provider, BHS phone call with Veteran, decision- tool sent to patient
Adherence Promotion			
Ordering treatment	Provider	Provider on Osteoporosis Order Set	BHS RN with provider co-signature

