### **Data Collection, Flow and Management**

Provider-level data is limited to demographic information and is collected on a paper form at the time of informed consent and entered into the study database. Paper forms are stored in the Durham GRECC as above.

Patient-level data from both Durham and Richmond VAMCs is downloaded directly from the Regional Data Warehouse on an excel spreadsheet, and uploaded into the study database behind the VA firewall. Additional data fields are abstracted by study staff from CPRS directly into the study database. The study database is maintained in a secure HSR&D drive folder <\\vhadurhsmcifs01.v06.med.va.gov\HSDR\PMOPS>. Data will not be transferred to outside entities.

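### Masked assessment is stated but not secured for the chart-abstracted parts of initiation, implementation, discontinuation and fractures, because the chart shows the Bone Health Service pathway

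*Protocol*

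**What the plan says.** The Design section of the Protocol, repeated in the SAP, says outcomes for eligible patients "will be assessed by investigators masked to group assignment via EHR at baseline and 2 years".

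Table 1 of the Protocol gives the sources:

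- Screening: "RDW at baseline, year 1 and year 2". No chart review.
- Initiation: "RDW, intervention period year 1 and year 2, non-VA medication lists by chart abstraction".
- Implementation and discontinuation: pharmacy dispensing records, again supplemented by chart-abstracted non-VA lists.
- Fractures (exploratory): "RDW, confirmed by chart abstraction".

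Under Data Collection, Flow and Management: "Additional data fields are abstracted by study staff from CPRS directly into the study database".

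Under BHS Screening Promotion, BHS men who meet a treatment threshold are referred to the bone health physician, who writes an e-consult; "this note is co-signed by the PACT provider". The BHS nurse then places the orders. Under BHS Adherence Promotion: "All patients initiating bisphosphonates will be called by the BHS RN at 1, 6, and 12 months". Table 2 leaves adherence monitoring in the control arm to the individual provider.

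**The concern.** An abstractor who opens the CPRS record of a BHS man in the initiation or adherence set would normally find an e-consult note that shows which arm he is in. Whether a non-VA list entry counts as a start or as continuing supply, and whether a coded fracture is confirmed, would then be judged with the arm in view.

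A second route does not depend on the abstractor. BHS starters have scheduled nurse contacts, while control follow-up is at the provider's choice. Outside medication could therefore be recorded more completely in BHS, and a perfectly masked abstractor would still count more of it there.

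Initiation and the adherence measures are Aim 1 outcomes, and Table 5 feeds them into the Aim 3 economic model. As the text stands, the report would describe all of these outcomes as masked.

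**Working it through.** The plan states no figure on this point, so there is nothing to reproduce. I compared the passages and then did scale arithmetic.

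**1. Which components are exposed**

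| Outcome | Base source | Chart component | Exposed? |
|---|---|---|---|
| Screening | Warehouse | None | No |
| Initiation | Warehouse | Non-VA medication lists | That supplement |
| Implementation, discontinuation | Dispensing records | Non-VA medication lists | That supplement |
| Fractures | Warehouse | Confirmation of the event | That step |
| Bone mineral density | DXA scan | None | No |

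**2. Is masking of abstraction described anywhere?** I found no redaction, separate abstraction staff, adjudication or check of masking in either document. The only other masking text concerns the statistician who randomized the teams, which protects allocation and not outcome assessment. The Protocol's section on the PACT Practice Management Model has the study team re-randomize and re-consent teams, so study personnel handle assignments. The Protocol does not separate them from the study staff who abstract.

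**3. How many BHS men carry the e-consult** (Protocol, Power and Table 6: 19 BHS and 20 control teams, average 100 patients each; screening 40% and 6%; 25% of screened men meet a threshold)

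- BHS patients: 19 × 100 = 1,900. Screened: 1,900 × 0.40 = 760. Meeting threshold: 760 × 0.25 = 190.
- Control patients: 20 × 100 = 2,000. Meeting threshold: 2,000 × 0.06 × 0.25 = 30.
- The 190 are the BHS initiation denominator, and the BHS starters used for adherence are a subset. All 190 are due an e-consult, less any men whose provider opts them out.
- For fractures the population is the whole panel, so the e-consult marks 190 / 1,900 = 10% of BHS men.

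**4. What differential capture could do to initiation.** Let p be true initiation, equal in both arms; s the share of starts recorded only as non-VA; c the proportion of those captured in each arm.

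Observed rate = p × [(1 − s) + s × c]

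Spurious difference = p × s × (c in BHS − c in control)

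The control value p = 55% is in Table 6. The documents give neither s nor the capture gap, so both are assumptions.

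| s | gap 20 points | gap 50 points | gap 100 points |
|---|---|---|---|
| 5% | 0.6 | 1.4 | 2.8 |
| 10% | 1.1 | 2.8 | 5.5 |
| 20% | 2.2 | 5.5 | 11.0 |

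Entries are percentage points. Lowest: 0.55 × 0.05 × 0.20 = 0.0055. Highest: 0.55 × 0.20 × 1.00 = 0.11. Table 1's important difference, a 30% increase from 55%, is 0.30 × 55 = 16.5 points if relative and 30 points if absolute. The extreme corner is thus 11 / 16.5 = 67% or 11 / 30 = 37% of it; the mildest is 0.55 / 16.5 = 3% or 0.55 / 30 = 2%.

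**The case against.** The best reply is that most of the data are electronic. The warehouse and dispensing records are the base, Table 1 names the one medication item to be abstracted, and the fracture review only confirms events already coded. All of that stands, and it limits the point to a supplement. It does not remove it: naming the item to abstract does not stop someone working in CPRS from seeing the rest of the record.

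One could also say that the masking sentence covers investigators, while staff do the abstraction. But the decision whether an entry counts is then made by the abstractor, so masking the investigators does not protect it.

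Several stronger readings are tempting, and the documents do not support them:

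- **That the four outcomes as a whole are chart-abstracted.** Table 1 contradicts this.
- **That nurse-call notes reveal the arm.** The calls are specified, but the text does not say they are written up in CPRS. The inference is reasonable, but the point does not need it, because the e-consult is expressly a note.
- **That fractures mentioned on BHS calls would add events.** A fracture must first appear in the warehouse, and the missing-data rule treats an absent code as no event. Nothing says a call creates a code.
- **That about five chart decisions could produce the whole important difference in initiation.** This takes 16.5 points over 30 control men (1/30 = 3.3 points each). It needs the relative reading of 30%, one year of screening, and control starts wrongly rejected. Read as absolute, 30 points is nine of 30 men. Over two years the denominator could approach 60, or 1.7 points each. In BHS, where extra recording would occur, one man is 1/190 = 0.5 points and 16.5 points takes about 31 men. Only men whose status turns on a non-VA entry are open to such a decision, and their number is not given.

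**Conclusion.** The concern holds for the chart-abstracted components only. The plan states masked assessment, describes no procedure that delivers it for non-VA medication entries or fracture confirmation, and places an arm-revealing note in the record being abstracted. The arm is readable for most of the roughly 190 BHS men in the initiation denominator, and for the starters among them. This rests on the Table 6 rates and on few provider opt-outs.

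More complete non-VA recording in BHS is a plausible mechanism, not one the documents state. The range of 0.6 to 11 points depends entirely on the two assumed inputs and is not an estimate of bias. A reader might infer that the initiation or adherence results are invalid; the documents do not support that.

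For fractures the point is weak: the outcome is exploratory and the e-consult marks about 10% of BHS men, although about 760 would have a DXA ordered through the service. No power or sample-size figure changes. The point is worth fixing because the remedy is cheap and the masking claim would otherwise be reported without support.

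**What to change.** 1. **Narrow the masking statement** in Design to outcomes read from the warehouse or dispensing records, and to abstraction done without access to arm.
2. **Give abstractors arm-neutral extracts only:** dated non-VA medication entries, and radiology or encounter reports for coded fractures. Leave out BHS notes and PACT identifiers, and use the same sources in both arms. State who abstracts.
3. **Add a sensitivity analysis** of initiation, implementation and discontinuation on VA warehouse and dispensing data alone, and of fractures on warehouse codes without chart confirmation. Step 2 hides the arm from the abstractor; only this step addresses entries that were recorded unequally in the first place. Read it beside the main result, not in its place: dropping non-VA data could itself favour BHS if control men more often start outside the VA.

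The cost is protocol wording, an extract specification, and a little programming and analysis. No additional patients are needed. The downside is some loss of context for the abstractor.

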## Adverse Events

Potential risks to PACT providers include disclosure of confidential demographic information, disruption or change of usual workflow, and emotional discomfort sharing information in a

nominal group technique session. Potential risks to the Veterans include disclosure of protected health information.

All adverse events will be reported per Durham VAMC requirements. All Serious, Unanticipated and Related adverse events will be reported to IRB within 5 business days of hearing of the event. All other adverse events will be reported at continuing review.

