### **Data and Safety Monitoring**

Although this is a low-risk study that is promoting guideline-recommended care, a data safety monitoring board will be recruited to include at least 1 ambulatory care clinician and 2 additional members from the Durham HSR&D COIN. The DSMB will meet biannually to review subject recruitment, data collection and management procedures, and safety outcomes. Screening rates at the PACT level will be measured at baseline and 2 years after implementation. Adverse drug effects related to osteoporosis medications will be evaluated by the DSMB every 6 months. Inadvertent data disclosures will be reported to the DSMB, IRB and VA ORD as soon as discovered, and immediate steps to minimize sharing will be taken.

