Screening Tool calculation. We do not expect attrition as new patients are added as others leave with relatively constant panel size. Finally, we determine power for the single degree of freedom contrast of import – Usual Care vs. BHS groups across the follow-up time points. For each of the individual outcomes, assumptions and power requirements are listed in the Table. A sample size of 39 PACTs (19 BHS vs. 20 Usual Care) with an average 100 patients / PACT provides over 85% power for all our primary patient-level outcomes, except fracture rates - an exploratory analysis.

Table 6. Power calculation assumptions for Aim 1

Outcome	Assumptions, Minimal Clinically Significant Difference	Power for 39 PACTs and 3900 patients
Screening Rates (PACT level)	6% Usual Care, 40% new models	>0.99
Osteoporosis Treatment	Assume 25% of screened meet treatment thresholds. 30% increase from 55% Usual Care	>0.99
Medication Adherence	Usual Care MPR 0.60 (SD 0.35). 20% increase	0.85
Bone Mineral Density (BMD) Femoral Neck in random sample of high-risk patients	0.939 g/cm  in BHS group vs. 0.967 Usual Care with SD pooled =0.133	0.90 for random sample of 952 patients (25/team); 0.80 for 712 (19/team)

**Missing data Strategies.** As is standard in administrative databases, the absence of a diagnosis code (e.g., fracture) will be assumed to indicate that the event did not occur, and coded by default as 'not present'. For continuous measures where zero is illogical, we will impute a value, simulate and use bootstrapping to derive estimates of effect with appropriate standard errors. To implement the multiple imputation techniques for primary analyses, we will use preliminary analyses of such associations, including graphical displays, to investigate the plausibility of the assumptions underlying the imputation model employed. Further, we will use 25 or more imputed data sets, with FU bootstrapped estimates in order to reduce the impact of the random sampling.

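### The benchmark of 1 per 50,000 patient-years for rare drug harms cannot be assessed in a trial that yields about 305 to 356 treated patient-years

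*Protocol*

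**What the plan says.** Table 1 (Protocol, Design; the SAP's Table 1 has the same row) names two serious drug harms, subtrochanteric fracture and osteonecrosis of the jaw. Both are identified from ICD-10 codes in the Regional Data Warehouse. The Important Difference column reads ">expected 1/50,000 patient years treatment". The row gives no source for the expected rate, no definition of a treated patient-year, and no expected count, test or confidence limit. The Power section does not cover harms, and the SAP's Revised Analysis Plan adds nothing on this row.

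Three other places bear on it:

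- The exploratory fracture row of Table 1 covers all clinical fractures except facial and digital ones. Its data source is "RDW, confirmed by chart abstraction" and its important difference is "10% decrease from 2.5/100 person years Control".
- Data and Safety Monitoring (Protocol) says: "Adverse drug effects related to osteoporosis medications will be evaluated by the DSMB every 6 months". No numerical criterion is attached.
- Table 5 (Aim 3) takes rare serious harms for the economic model from population data, not from this trial.

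**The concern.** A rate of 1 per 50,000 patient-years can be judged only with exposure on a comparable scale. A pragmatic trial in 39 primary care teams, in which only a fraction of men are screened and a fraction of those treated, will not come near it. If the row is applied as written, a single coded event is an excess and no event is no excess, and neither label says much about the drug-related rate. A sentence in the final report that rare harms did not exceed expectation would meet the written criterion with almost no evidence behind it.

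The coded event is also broader than the harm of interest. A subtrochanteric fracture code does not separate an ordinary fracture in an older man from one related to treatment.

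**Working it through.** The harm row contains no calculation, so there is no figure of the plan's to reproduce. The check builds treated exposure from the plan's other assumptions.

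**Inputs (Protocol, Power and Table 6, unless noted)**

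- Size: "A sample size of 39 PACTs (19 BHS vs. 20 Usual Care) with an average 100 patients / PACT", so 1,900 BHS men and 2,000 usual-care men.
- Screening: "6% Usual Care, 40% new models".
- Treatment: "Assume 25% of screened meet treatment thresholds. 30% increase from 55% Usual Care". The 30% increase can be read as relative (55% × 1.3 = 71.5%) or absolute (85%); both are carried through.
- Follow-up: 2 years (Specific aims).
- Assumption: every treated man contributes the full 2 years. Staggered starts and non-adherence would reduce this.

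**Treated men**

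- BHS: 1,900 × 0.40 × 0.25 × 0.715 = 135.9, or × 0.85 = 161.5.
- Usual care: 2,000 × 0.06 × 0.25 × 0.55 = 16.5.
- Total: 152.4 to 178.0.

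**Treated patient-years (PY):** 152.35 × 2 = 304.7, and 178 × 2 = 356. Usual care supplies only 16.5 × 2 = 33 of these, so a comparison between arms is uninformative as well.

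**Formulas (exact Poisson, benchmark 1/50,000)**

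- Expected events at the benchmark: PY / 50,000.
- One event as a multiple of the benchmark: 50,000 / PY.
- One-sided 95% upper limit with zero events, as a multiple: 2.996 × 50,000 / PY.
- Chance of at least one event if the true rate is k times the benchmark: 1 − exp(−k × PY / 50,000).

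| Scenario | PY | Expected events | One event | Upper limit, zero events | P(≥1) at benchmark | P(≥1) at 10× |
|---|---|---|---|---|---|---|
| 71.5% started, 2 years | 304.7 | 0.0061 | 164× | 492× | 0.6% | 5.9% |
| 85% started, 2 years | 356 | 0.0071 | 140× | 421× | 0.7% | 6.9% |
| 85% started, two full screening rounds, 4 years per man (assumed) | 1,424 | 0.028 | 35× | 105× | 2.8% | 25% |
| All 3,900 men treated for 5 years (ceiling) | 19,500 | 0.39 | 2.6× | 7.7× | 32% | n/a |

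The third row doubles the treated men to 323 + 33 = 356 and gives each 4 years: 356 × 4 = 1,424. The fourth cannot be reached in practice; it shows that the conclusion does not turn on the exposure assumption. In the other direction, scaling 356 by the usual-care possession ratio of 0.60 gives 214 patient-years, and one event is then 234 times the benchmark.

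For zero events to bring the upper limit down to the benchmark, 2.996 × 50,000, or about 150,000 treated patient-years, would be needed.

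**Ordinary fractures.** At 2.5 per 100 person-years there are 0.025 × 50,000 = 1,250 clinical fractures per 50,000 person-years. Ordinary subtrochanteric fractures alone pass the benchmark if they exceed 1/1,250 = 0.08% of clinical fractures. The documents do not give that share. Applying the control rate to treated men (an assumption), 305 to 356 patient-years contain about 7.6 to 8.9 clinical fractures. For assumed shares of 0.5%, 1% and 2%, the chance of at least one ordinary subtrochanteric fracture is about 4%, 7 to 9% and 14 to 16%.

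**The case against.** The best defence is that the figure does less than its column suggests. No test, stopping rule or DSMB trigger is tied to it, and the economic model does not use the trial's count. All of that stands. A reader might infer that the DSMB is left unable to act; the documents do not say so, because nothing confines its 6-monthly review to this figure and it can consider a single case.

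It is also too strong to say that the criterion gives no information. If the coded event were purely drug-related and the true rate equalled the benchmark, a false alarm would have a probability of only 0.6 to 0.7% (2.8% at 1,424 patient-years). One event would put the one-sided 95% lower limit, 0.0513 × 50,000 / PY, at 7.2 to 8.4 times the benchmark (1.8 times at 1,424). Zero events does exclude extremely high rates. What fails is sensitivity and reassurance: at ten times the benchmark, the chance of seeing no event is still about 93 to 94%. The false-alarm part rests on the share of ordinary subtrochanteric fractures, which has to be assumed.

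Two further readings are tempting and are not supported:

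- That subtrochanteric fractures go unconfirmed. They are neither facial nor digital, so the exploratory fracture row already has them chart-confirmed. Only jaw osteonecrosis rests on codes alone. What remains is that the harm row cites codes as its source, so one table allows two different counts of the same fracture.
- That the Adverse Events section sends these harms down a conflicting reporting route. It says "Potential risks to the Veterans include disclosure of protected health information", but the verb does not make the list exhaustive, and the section does not define what counts as unanticipated. The conflict would be the reader's inference.

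**Conclusion.** The point holds in this form: the important difference for subtrochanteric fracture or jaw osteonecrosis cannot be assessed in this trial. On the plan's inputs over 2 years the criterion becomes any event versus none, with one event at about 140 to 164 times the benchmark and zero events bounded only at about 420 to 492 times it. The exposure figures rest on the Table 6 rates being met and on full 2-year exposure. The 1,424 patient-year case needs assumptions beyond the documents' horizon, and even there the multiples are 35 and 105.

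The consequence is limited to what the trial may say about rare harms. Efficacy conclusions and the Aim 3 inputs are untouched. It is still worth correcting, because the present wording would license an unsupported statement of no excess and would label a single ordinary fracture an excess.

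**What to change.** In the harm row of Table 1, in both Protocol and SAP:

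1. Remove 1/50,000 as the important difference and label the row descriptive. If the figure is kept as background, give its source and the event it refers to.
2. Report counts by arm and by treatment exposure, with treated patient-years and exact Poisson limits.
3. State that the trial can neither confirm nor exclude the expected rate.
4. Take the subtrochanteric component from the chart-confirmed fracture data, recording drug exposure and trauma, and extend the same abstraction to coded jaw osteonecrosis.
5. List confirmed cases in treated men individually in the existing 6-monthly DSMB review.

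The cost is document wording and a handful of extra abstractions by staff who already abstract fractures. The downside is a weaker stated safety claim, which is all that the exposure can support.
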